Inclusion criteria	
 • Able to provide written informed consent before any study-specific assessment is performed • Male or female ≥ 18 years of age with body weight ≥ 40 Kg and ≤ 160 Kg. • Systolic blood pressure ≥ 125 mmHg at the beginning of the screening period (after ICF signature) and at the end of the screening period (prior to randomization) • Admitted/hospitalized for AHF. AHF is defined as including all of the following measured at any time between presentation and the end of screening: 
 • Persistent dyspnea at rest or with minimal exertion, at screening and at the time of randomization, despite standard background therapy for acute decompensated heart failure including intravenous furosemide of at least 40 mg total (or equivalent) • Pulmonary congestion assessed through physical examination and chest X-Ray obtained during routine clinical practice at any time between presentation and the end of screening (prior to randomization) • BNP ≥ 500 pg/mL or N-terminal pro b-type natriuretic peptide (NT-proBNP) $\geq 2,000$ pg/mL. For patients treated with valsartan/sacubitril (Entresto®), BNP is not a suitable biomarker and only NT-pro-BNP should be assessed • Able to be randomized within 16 hours from presentation to the hospital [presentation starts as the earliest of (1) time of presentation at either the ER/ED, ICU/CCU or ward; or (2) time of first IV loop diuretic for treatment of the current AHF episode prior to arrival at the hospital (this includes outpatient clinic, ambulance, or hospital including emergency department)] • Received intravenous furosemide of at least 40 mg (or equivalent) at any time between presentation and the start of screening for the study • Impaired renal function defined as an estimated glomerular filtration rate (eGFR) between presentation and randomization defined as ≥ 25 and ≤ 75 mL/min/1.73 m², calculated using the simplified Modification of Diet in Renal Disease (sMDRD) equation.

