4.1 Inclusion criteria

Subjects must fulfill **all** of the following criteria at screening to be eligible for the study. The screening period is defined as that interval that begins at the time the informed consent is signed and ends with the qualification of the subject for entry into the study (i.e. when subject has met all eligibility criteria):

1. Able to provide written informed consent before any study-specific assessment is performed. The AHF diagnostic assessments performed as per current local institution/hospital standard practice or as part of routine clinical care can be used to support patient screening even if performed before obtaining informed consent.
2. Male or female \geq 18 years of age with body weight \geq 40 Kg and \leq 160 Kg.
3. Systolic blood pressure \geq 125 mmHg at the beginning of the screening period (after ICF signature) and at the end of the screening period (prior to randomization).
4. Admitted/hospitalized for AHF. AHF is defined as including all of the following measured at any time between presentation and the end of screening:
 - a. Persistent dyspnea at rest or with minimal exertion, at screening and at the time of randomization, despite standard background therapy for acute decompensated heart failure including intravenous furosemide of at least 40 mg total (or equivalent)
 - b. Pulmonary congestion assessed through physical examination and chest X-Ray obtained during routine clinical practice at any time between presentation and the end of screening (prior to randomization)
 - c. N-terminal pro B-type natriuretic peptide (NT-proBNP) \geq 2,000 pg/mL or BNP \geq 500 pg/mL. For patients treated with valsartan/sacubitril (Entresto®), BNP is not suitable and only NT-pro-BNP should be assessed
5. Able to be randomized **within 16 hours** from presentation to the hospital [presentation starts as the earliest of (1) time of presentation at either the ER/ED, ICU/CCU or ward; or (2) time of first IV loop diuretic for treatment of the current AHF episode prior to arrival at the hospital] *(this includes outpatient clinic, ambulance, or previous hospital including emergency department).*

6. Received intravenous furosemide of at least 40 mg (or equivalent) at any time between presentation and the start of screening for the study

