5.1 Protocol requested treatment

5.1.1 Investigational treatment

Serelaxin will be administered according to a weight-range adjusted dosing regimen at a nominal dose of 30 µg/kg/day (refer to the details in [Section 5.5.4](#)), as a continuous intravenous infusion for 48 hours. The study drug is provided as a 1 mg/mL solution in 6 mL vials (with 3.5 mL fill). For the randomized patients to receive the study drug infusion, it will be withdrawn from the vials contained in the kits, injected into a 250 mL intravenous bag of 5% dextrose solution and then infused through a dedicated IV line or port, using compatible tubing, infusion filters and IV bags according to instructions in the *Pharmacy Manual*.

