The study drug kits, allocated to each randomized patient via IRT, containing one 6 -mL vial of serelaxin (with 3.5 mL fill), will be used to compound study drug for the first 24 hours of infusion for all patients <115 kg in weight; in cases when the subject is ≥ 115 kg, two study drug kits will be assigned via IRT for the first 24 hours of infusion. The body weight determined between presentation and randomization, rounded up to the nearest 0.5 kg, will be used for the calculation of the dose for each patient, for the entire 48-hour infusion period. Study drug from a second kit or pair of kits, also assigned via IRT depending on the patient's body weight as assessed between presentation and randomization, will be used to continue the infusion for the second 24 hours. The second study drug kit should be obtained by calling IRT close to the end of the 1st 24 hours of study drug infusion.

Table 5-1 Weight-range adjusted dosing regimen of serelaxin

Body weight (kg)	Serelaxin (mg)	Volume of serelaxin to be added to 250 mL IV bag of sterile 5% dextrose for intravenous infusion over a period of 24 hours
40-59 kg	2.0 mg	2.0 mL
60-74 kg	3.0 mg	3.0 mL
75-114 kg	3.5 mg	3.5 mL
115-160 kg	5.5 mg	5.5 mL (2 vials needed)

All kits of investigational treatment assigned by the IRT will be recorded in the IRT.

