6.5.3 Height and weight

Height in centimeters (cm) or inches (inch) will be measured at screening only.

Body weight (to the nearest 0.1 kilogram [kg] or 0.1 pounds [lbs] in indoor clothing, but without shoes) will be measured at Screening and at 24 and 48 hours after study drug infusion in serelaxin arm, and daily through index hospitalization, at discharge, and at Day 5 and then at Day 14. For the SOC patients, body weight will be measured at screening, 24 and 48 hours after randomization and daily through index hospitalization, at discharge, and at Day 5, and then at Day 14. These measurements during hospitalization can be performed at any time of the day.

If patient's body height/weight cannot be measured at Screening because of the patient's physical condition, verbal height/weight will be acceptable. Height/weight measurements shall be obtained as soon as the patient is physically able.

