Exclusion criteria	Current or planned treatment with any IV vasoactive therapies or mechanical support, with the exception of IV furosemide (or equivalent diuretic) or IV nitrates at a dose of ≤ 0.1 mg/kg/hour if the patient has a SBP >150 mmHg at the start of the screening (Exclusion criteria #5)	EC004 EC004_M1 EC004_A1 EC004_M2					X
	Significant left ventricular outflow obstruction, uncorrected, such as obstructive hypertrophic cardiomyopathy or severe aortic stenosis severe aortic regurgitation and severe mitral stenosis (Exclusion criteria #6)	EC007 EC008_M1 EC009_M1 EC010_M1					X
	Clinical evidence of acute coronary syndrome currently or within 30 days prior to enrollment. (Exclusion criteria #7)	EC011					X
	AHF due to significant arrhythmias, which include any of the following: sustained ventricular tachycardia, bradycardia with sustained ventricular rate <45 beats per minute or atrial fibrillation/flutter with sustained ventricular response of >130 beats per minute (Exclusion criteria #8)	EC012 EC013 EC014					X

	Statistical Analysis Plan
	Sponsor: NOVARTIS
	Protocol number: CRLX030A3301

Category	Description	Code(s) *	Exclusion from analysis set				
			SCR	RAN	FAS	PP	SAF
Treatment deviation	Drug infusion not administered according to a weight-range adjusted dosing regimen at the nominal dose of 30 µg/kg/day.	DRUG02 DRUG02_A3 DRUG03					X
	Study drug not injected into a 250 mL intravenous bag of 5% dextrose solution or not infused through a dedicated IV line or port, using compatible tubing, infusion filters and IV bags or not following instructions in the Pharmacy Manual.	DRUG05					X
	Investigational treatment not handled and stored properly (including temperature control).	DRUG06					X
	Expired investigational treatment	DRUG07					X
	Serelaxin infusion began later than 4 hours after start of study drug preparation.	DRUG011					X
	Serelaxin administered despite patient randomized in SOC arm	DRUG12					X
	Serelaxin administered despite patient not randomized with IRT	DRUG13		X	X	X	
	Serelaxin not administered despite patient randomized in Serelaxin arm and SBP pre-infusion ≥ 100 mmHg.	DRUG14					X X
Other	Subject does not undergo any clinical evaluations of AHF signs/symptom and subject does not report any information about the need for further IV or oral HF treatment and about the occurrence of worsening HF events through Day 5	PROC03					X
	Subject does not perform the scheduled visit at Day 5	PROC03_A1					X

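### Dosing weight is rounded up to 0.5 kg but the dose bands are in whole kilograms, so rounded weights of 59.5 and 74.5 kg have no dose row, and near 115 kg the dose table and the kit rule can disagree.

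*Protocol*

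**What the plan says.** - **Eligibility.** The protocol synopsis, matching inclusion criterion 2 in section 4.1, admits "Male or female ≥ 18 years of age with body weight ≥ 40 Kg and ≤ 160 Kg". Every weight in that range is eligible.
- **Measurement.** Protocol 6.5.3 asks for "Body weight (to the nearest 0.1 kilogram [kg] or 0.1 pounds [lbs] in indoor clothing, but without shoes". A verbal weight is accepted if the patient cannot be weighed at screening.
- **Rounding.** Protocol 5.5.4 says that the weight obtained between presentation and randomization, "rounded up to the nearest 0.5 kg, will be used for the calculation of the dose for each patient", for the whole 48-hour infusion.
- **Dose table.** Table 5-1 assigns 2.0 mg per 24 hours at 40-59 kg, 3.0 mg at 60-74 kg, 3.5 mg at 75-114 kg and 5.5 mg at 115-160 kg. The last row is marked "5.5 mL (2 vials needed". SAP Table 2.4-1 repeats the bands, and the SAP gives no rounding rule.
- **Vials and kits.** On the vials, Protocol 5.1.1 states: "The study drug is provided as a 1 mg/mL solution in 6 mL vials (with 3.5 mL fill". Each kit holds one vial. Under 5.5.4, one kit is used "for the first 24 hours of infusion for all patients <115 kg in weight", and two kits are assigned at 115 kg or more. The kit rule does not mention rounding. For the second 24 hours it refers to the weight as it was assessed.
- **Deviation code.** SAP Table 3-1 lists, under DRUG02, "Drug infusion not administered according to a weight-range adjusted dosing regimen at the nominal dose of 30" µg/kg/day.

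**The concern.** A rule that produces half-kilogram weights is paired with a table that has no half-kilogram entries at its internal boundaries. For some eligible patients the stated rule therefore returns no dose. Neither document says that a band runs up to the start of the next one.

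Kit allocation cannot fill the two lower gaps. At 59.5 kg the candidate volumes are 2.0 and 3.0 mL, and at 74.5 kg they are 3.0 and 3.5 mL. All of them come from a single 3.5 mL vial, so two sites could choose different rows and nothing in the kit system would show it.

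Just below 115 kg the problem is different. The table and the kit rule can give incompatible instructions, depending on which weight the kit rule uses.

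What is at stake is consistent dosing between sites, and a clear test for DRUG02 when the per-protocol set is formed.

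**Working it through.** **Inputs.** Eligible range 40-160 kg (Protocol 4.1); resolution 0.1 kg (6.5.3); rounding up to 0.5 kg, the bands and the kit cut-off at 115 kg (5.5.4 and Table 5-1); 3.5 mL per vial at 1 mg/mL (5.1.1).

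**Step 1: reproduce the table's vial count.** Vials = dose volume / 3.5 mL, rounded up to a whole number. For 2.0, 3.0, 3.5 and 5.5 mL this gives 1, 1, 1 and 2, which agrees with Table 5-1.

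**Step 2: look up every dosing weight.** From 40.0 to 160.0 kg in steps of 0.5 there are (160 - 40)/0.5 + 1 = 241 possible rounded weights. Exactly three have no row. The ends of the range are covered: 40.0 stays at 40.0, and 159.6-160.0 becomes 160.0.

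| Rounded weight | Measured weights leading to it | Adjacent rows, mg per 24 h | Ratio | µg/kg/day |
|---|---|---|---|---|
| 59.5 kg | 59.1-59.5 | 2.0 or 3.0 | 3.0/2.0 = 1.50 | 33.6 or 50.4 |
| 74.5 kg | 74.1-74.5 | 3.0 or 3.5 | 3.5/3.0 = 1.17 | 40.3 or 47.0 |
| 114.5 kg | 114.1-114.5 | 3.5 or 5.5 | 5.5/3.5 = 1.57 | 30.6 or 48.0 |

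The last column is dose in µg divided by weight, for example 2000/59.5 = 33.6. At 114.5 kg both the measured and the rounded weight are below 115 kg. One kit is supplied, and 5.5 mL cannot be drawn from 3.5 mL. The table row is still missing, but the choice is in effect limited.

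**Step 3: compare the table with the kit rule.** Measured weights of 114.6-114.9 kg round up to 115.0 kg, so the row is 5.5 mL from two vials.
- Kit rule on measured weight (below 115 kg): one kit, 3.5 mL, which is 5.5 - 3.5 = 2.0 mL short.
- Kit rule on rounded weight (115.0 kg): two kits, no conflict.

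**Step 4: other readings of the rounding rule.** If it means ordinary rounding to the nearest 0.5 kg, the same three values lack a row and the possible kit conflict narrows to 114.8-114.9 kg. With no rounding, the gaps widen to 59.1-59.9, 74.1-74.9 and 114.1-114.9 kg.

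**Step 5: how many patients (assumption, not from the documents).** With 2:1 allocation of 3,183 patients, 3,183 × 2/3 = 2,122 receive serelaxin. Assume normally distributed weight and take each gap as a half-kilogram interval (59.0-59.5, 74.0-74.5, 114.0-114.5).

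| Mean, SD (kg) | Two lower gaps | All three gaps | All three × 2,122 | 114.5-115.0 kg × 2,122 |
|---|---|---|---|---|
| 75, 16 | 2.01% | 2.07% | 44 | 1 |
| 80, 18 | 1.62% | 1.80% | 38 | 4 |
| 85, 20 | 1.30% | 1.64% | 35 | 7 |

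**The case against.** **The bands are obviously contiguous.** The split at 115 kg in the kit rule suggests that each band runs to just below the next. This is a natural reading and it settles most of the 114.5 kg case. It is not written down, however, and it leaves the possible conflict at 114.6-114.9 kg. At 59.5 and 74.5 kg the kit rule says nothing that would support it.

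**The kit conflict is conditional.** This stands. It arises only if kits are assigned on measured weight while the dose is prepared on rounded weight. The text permits that combination but does not state it.

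**Other documents may settle it.** The Pharmacy Manual, the IRT specification and the Protocol Deviation Handling Document were not available and may do so. The protocol nevertheless states the dose rule itself, and neither it nor the SAP closes the gaps.

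**The doses in question are not extreme.** This largely stands. Table 5-1 already gives patients inside its bands from 3500/114 = 30.7 to 2000/40 = 50.0 µg/kg/day. The disputed values, 30.6 to 50.4, lie almost entirely within that spread. A reader might infer from the hypotension risk that gap patients face exposure beyond what the plan accepts; the table's own figures do not show that.

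**The patient count is soft and probably high.** This stands. Verbal weights are accepted and may cluster on whole kilograms, which never fall in a gap. Amendment 4 also reports 2,337 patients already randomized. That left 3,183 - 2,337 = 846, or 846 × 2/3 = 564 on serelaxin; at 1.64-2.07% a correction from then on could reach about 9 to 12 patients.

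**Conclusion.** The rounding rule and the dose table do not fit together. Two rounded weights, 59.5 and 74.5 kg, have no dose row, and nothing else in the documents decides between rows that differ by 50% and 17%. A third, 114.5 kg, also lacks a row, but the one-kit rule in effect limits the choice, so the 57% difference there should not be presented as an open one. At 114.6-114.9 kg the dose table and the kit rule conflict only if kits are assigned on measured weight.

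The consequences are possible inconsistent dosing between sites for a small share of serelaxin patients, and an unclear DRUG02 decision for the per-protocol set. The share cannot be derived from the documents; the figure of about 2% rests on an assumed normal weight distribution.

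A reader might infer that the efficacy result or the exposure reporting is compromised. The documents do not support that. The primary analysis uses the FAS as randomized, and the per-protocol analysis is supportive only. The SAP's exposure summary uses recorded prescribed dose, volume, rate and duration, none of which needs a lookup in the weight bands. Nor does it follow that per-protocol membership as a whole becomes arbitrary: only the DRUG02 call for patients at these weights is unclear, and the deviation handling document may resolve it.

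The point merits correction because the rule fails for eligible patients and the repair is simple.

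**What to change.** Reconcile four items: the rounding rule in Protocol 5.5.4, Table 5-1, SAP Table 2.4-1 and the kit rule.

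1. Write the bands as contiguous intervals that together cover 40-160 kg, with explicit inclusive and exclusive limits.
2. Name one weight, measured or rounded, and use it for both the dose table and the kit rule, in each 24-hour period.
3. Leave the row for each gap to the sponsor's clinical team; no dose or band limit is proposed here.
4. Check that the IRT specification and the Pharmacy Manual agree with the reconciled text.
5. Apply DRUG02 against the reconciled table.

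The cost is a table and wording correction in the protocol and SAP, plus a check of the IRT and Pharmacy Manual. Visits, assessments and sample size do not change.

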5.5.5 Permitted dose adjustments and interruptions of study treatment

Systolic Blood Pressure (SBP) has to be ≥ 125 mmHg for the patient to be eligible, and then ≥ 125 mmHg during the screening period, in particular at the end of the screening period just before calling the IRT for randomization. In many centers, continuous cardiac monitoring will probably be applied and this will keep the site informed about SBP values.

Considering the high fluctuation of blood pressure in patients with decompensated HF, especially because the patient might be under the effect of nitrates (even at low dose) and diuretics, it is advised to minimize the time windows between the end of screening, the IRT call and start of the serelaxin infusion.

In practice:

- BP has to be measured at the end of screening and SBP must be ≥ 125 mmHg before calling the IRT. Once the patient is randomized, the study drug should be prepared promptly (if the patient is in the serelaxin group).
- Just before the immediate start of study drug infusion, SBP must be assessed again. During that interval between randomization and infusion start, sometime will elapse (30 to 60 minutes in most cases) and BP may fluctuate.
 - It is not required that pre-infusion SBP be ≥ 125 mmHg (SBP ≥ 125 mmHg is an inclusion criterion and matters only up to randomization)
 - If at the immediate start of study drug infusion, SBP is below 100 mmHg (SBP < 100 mmHg), serelaxin should not be started, neither now nor later. The patient will remain in the study up to 30 days but will not have received serelaxin
 - If a blood pressure fall has occurred since randomization but SBP is still ≥ 100 mmHg, the decision to start or not the infusion remains at the discretion of the investigator, based on the hemodynamic context of the patient (i.e. previous hemodynamic stability, DBP, concomitant medications, medical response to IV furosemide/diuretics, etc.).

Of note, there is no mandatory time window between randomization and start of the study drug infusion. This time span should be kept as short as possible. For microbiological reasons, there is a maximum time of 4 hours allowed between preparation (mixing) of the study drug and infusion start.

If at any time during the study drug infusion, the subject's systolic blood pressure decreases by >40 mm Hg from just before the study drug infusion but is ≥ 100 mmHg in two consecutive measurements 15 min apart, the serelaxin infusion rate will be decreased by 50% for the

remainder of the 48-hour study drug administration. Serelaxin administration will be permanently discontinued at any time if in 2 consecutive measurements; 15 minutes apart, systolic blood pressure is reduced to <100 mmHg.

Table 5-2 describes the actions required for a systolic BP decrease during the period of study drug infusion, which must be strictly followed.

Table 5-2 Dosing adjustment of study drug administration in the event of systolic BP decrease through completion of study drug infusion

Changes in systolic BP during infusion*	Adjustments of study drug administration
Decrease >40 mmHg from pre-treatment (i.e., measured just before the immediate start of study drug infusion), but systolic BP remains ≥ 100 mmHg	Reduce the infusion rate by half for the remainder of the study drug administration, i.e., reduce infusion rate from 10 mL/hour to 5 mL/hour for the remainder of 48-hour infusion
Decrease in absolute value of systolic BP to <100 mmHg	Permanently terminate study drug infusion

* These systolic BP values should be confirmed by two measurements taken 15 minutes apart.

In addition, dosing may be discontinued at any time at the discretion of the investigator. Reasons the investigator may discontinue study drug administration include, but are not limited to, serious or intolerable AEs suspected to be related to study drug. If dosing is discontinued for BP decreases, or any safety reasons, it should not be restarted. Re-administration of study drug once terminated for safety reasons is not allowed. The total time from initiation of study drug infusion to completion must not exceed 48 hours. In the event that study drug administration is discontinued, regardless of the reason, the patient will continue to be followed at all study visits defined in the protocol. These changes in study drug dose must be recorded on the Dosage Administration Record eCRF.

5.5.6 Rescue medication

The investigator may prescribe any medications and/or supportive care during the study based on clinical needs. Use of rescue medication must be recorded on the Concomitant medications/Significant non-drug therapies in the eCRF.

5.5.7 Concomitant treatment

To be eligible for the study, all patients must have received IV furosemide of at least 40 mg (or equivalent e.g. Torasemide 20 mg or Bumetanide 2 mg) at any time between presentation and the start of screening for the study. This total 40 mg IV furosemide or equivalent loop diuretic dose might include the dose that the patient has received in the emergency service ambulances.

Patients will not be enrolled in the study if concomitant therapy for AHF includes current (within 2 hours prior to randomization) or planned (through the completion of study drug infusion) treatment with any cardiovascular IV therapies, including vasodilators (including nesiritide), positive inotropic agents and vasopressors, or mechanical support (intra-aortic balloon pump, endotracheal intubation, assisted (invasive or non-invasive) ventilation, or any

ventricular assist device), with the exception of IV nitrates at a dose of ≤ 0.1 mg/kg/hour if the patient has a systolic BP > 150 mmHg at the start of the screening. Use of IV furosemide (at least 40 mg or equivalent) is an inclusion criterion. Further doses of IV or oral furosemide can be administered at any time after enrollment.

The investigator may prescribe any additional medications during the study as made necessary by the patients' condition. Administration of any standard AHF treatment shall in no instance be delayed or withheld due to patient's participation in the study. Standard AHF treatment includes, but is not limited to, administration of the major classes of cardiovascular medications, as well as administration of oxygen, analgesics, anxiolytics and sedatives, as needed.

Heart failure medications, procedures and significant non-drug therapies administered after the patient was enrolled into the study must be recorded. The investigator shall instruct the patient to notify the investigator or associated study personnel about any new medications he/she takes after discharge and up to Day 30.

Administration of any cardiovascular IV therapies, including vasodilators (including nesiritide), positive inotropic agents and vasopressors, or mechanical support (intra-aortic balloon pump, endotracheal intubation, assisted ventilation (invasive or non-invasive), or any ventricular assist device), is allowed when necessary in both groups. However, in the serelaxin group caution should be exercised and potential additive hypotensive effects be discussed, in order to decide whether to maintain or discontinue the serelaxin infusion during administration of the above mentioned additional AHF drugs or procedures.

Any concomitant treatment taken by a subject during the hospital stay and until Day 30 will be recorded.

